## 2. Association of CIAKI with clinically meaningful, patient-centered outcomes

### a. *Short-term mortality associated with CIAKI*

Observational studies demonstrate an association between CIAKI (defined by small absolute and/or relative changes in SCr) and increased short-term mortality. In a retrospective study, Levy et al. found that the incidence of in-hospital death among 183 hospitalized patients who developed CIAKI (defined by an increase in SCr of  $\geq 25\%$  to at least 2.0 mg/dL) was 34% compared to 7% in 174 matched controls without CIAKI (unadjusted OR=6.5,  $p < 0.001$ ). In analyses that accounted for underlying severity of illness, CIAKI remained a strong predictor of in-hospital death (OR=5.5,  $p < 0.001$ ). A subsequent study by McCullough et al. of 1,826 patients who underwent percutaneous coronary intervention (PCI) found an incidence of in-hospital mortality of 7.1% among patients who developed CIAKI (defined by an increase in SCr of  $> 25\%$ ) compared to 1.1% in those without this change in SCr ( $p < 0.0001$ ). In patients who developed CIAKI that required renal replacement therapy, in-hospital mortality was 35.7%. Six additional studies, including an analysis by our group of over 27,000 patients reported an independent association of CIAKI with short-term mortality (Table 2).

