## 2. Exclusion criteria

- Currently receiving hemodialysis, peritoneal dialysis, continuous renal replacement therapy, or sustained low efficiency dialysis (SLED)
- Stage 5 CKD (eGFR  $<15$  mL/min/1.73 m^2)
- Unstable baseline SCr (if known) at the time of angiography defined by a change in SCr of  $\geq 25\%$  over the 3 days prior to angiography
- Decompensated heart failure requiring any of the following therapies at the time of angiography (we are excluding these patients because IV fluid administration may be contraindicated):
  - IV milrinone, inamrinone, dobutamine, or nesiritide
  - Isolated ultrafiltration therapy
  - Intra-aortic balloon pump
- Emergent angiography procedures defined as an anticipated duration of  $<3$  hours between the identification of the indication for angiography and the time of the planned procedure. We are excluding these patients due to the limited time to collect necessary research data and to ensure that research procedures do not interfere with time-sensitive clinical care.
- Receipt of intravascular iodinated contrast within the 5 days preceding angiography
- Receipt of oral or IV NAC within the 48 hours preceding angiography
- Known allergy to NAC
- Known anaphylactic allergy to iodinated contrast media

- Age <18 years
- Pregnancy
- Prisoner
- Ongoing participation in an unapproved concurrent interventional study

Eligible patients who indicate at the time of recruitment an unwillingness to comply with the 96-hour and 90-day outcome assessments will also be excluded.

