## 2. Primary study outcome

The primary outcome will be a composite of serious, adverse, patient-centered events, including death, need for acute dialysis, or persistent decline in kidney function within 90 days following angiography. These outcomes, which we refer to as major adverse kidney events and death (MAKE-D) will be defined as follows:

- **Death** based on medical record and/or vital status registry documentation.
- **Need for acute dialysis** defined as the initiation of any modality of renal replacement therapy

[figure not shown]
(intermittent hemodialysis, peritoneal dialysis, continuous renal replacement therapy, or sustained low-efficiency dialysis) within 90 days of the index angiographic procedure.

- **Persistent decline in kidney function** defined by an increase in SCr from the baseline value of at least 50% at 90 days following the index angiographic procedure. This outcome will be based on a comparison of the pre-angiography and 90-day SCr values analyzed at the central laboratory.

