The need for dialysis as a component of our primary composite outcome refers to acute dialysis that may or may not lead to the chronic long-term requirement for renal replacement therapy. Given that we are proposing to enroll patients with Stage 3 and Stage 4 CKD (baseline eGFR 15-60 ml/min/1.73 m^2), it would be unexpected for these patients to progress to ESRD and need chronic dialysis within the 90-day follow-up period without an acute change in the trajectory of their chronic kidney disease. For patients who require acute dialysis in the setting of AKI, failure to recover kidney function within 90 days is the conventionally accepted transition from acute dialysis to end-stage renal disease and "chronic" dialysis. Thus, the need for dialysis within 90 days of contrast administration as a component of the primary outcome in this study is, by definition, acute dialysis. Patients who require acute dialysis following an episode of CIAKI may: i) experience a full or partial recovery of kidney function obviating the need for continued dialysis therapy; ii) develop ESRD necessitating chronic renal replacement therapy; or iii) die within 90 days before meeting the definition of ESRD/chronic dialysis. While CIAKI resulting in death or the need for chronic dialysis (i.e., ESRD) is relatively uncommon, the clinical significance of such outcomes is unequivocal. Less well recognized are the important adverse short and long-term implications of AKI that requires acute transient dialysis. Acute temporary dialysis, either with intermittent hemodialysis or continuous renal replacement therapy, is associated with important short-term adverse outcomes, including bleeding and blood-borne infection related to dialysis catheter placement, hemodynamic instability due to fluid and solute shifts during the dialysis procedure, and financial costs that may exceed \$500 to \$1,000 per treatment. Two recently published large studies demonstrated the longer-term implications of

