acute temporary dialysis following an episode of AKI. Wald et al. conducted a population-based cohort study comparing long-term outcomes of 3,769 patients who developed AKI that required temporary dialysis with 13,598 matched controls who were hospitalized, but did not develop AKI. At a median of 3 years of follow-up, the risk for ESRD was more than 3-fold higher among patients who required acute transient dialysis compared to severity of illness matched controls (adjusted HR 3.23; 95% CI: 2.70-3.86). Another study by Lo and colleagues examined the association of AKI that required transient dialysis with progression of CKD and mortality. Among 562,799 hospitalized patients who had a baseline eGFR  $\geq 45$  ml/min/1.73 m^2, 703 sustained dialysis-requiring AKI, of whom 295 (42%) died, 65 (9%) remained chronically dialysis dependent, and 343 (49%) recovered sufficient kidney function to be able to discontinue dialysis by the time of hospital discharge. In multivariate analyses, AKI requiring transient dialysis was associated with a 28-fold increased risk of developing progressive CKD, defined as a decline in kidney function to an eGFR  $\leq 30$  ml/min/1.73m^2, and a 2-fold increase risk of death over 6 years of follow up. Thus, the need for acute transient dialysis following an episode of AKI has substantial short and long-term clinical implications and represents a clinically important component of our primary composite endpoint.

*c. Justification for inclusion of persistent decline in kidney function in primary endpoint*

A series of recent studies demonstrated robust associations of CIAKI with persistent renal injury and with an acceleration in the long-term rate of decline in kidney function. We propose to include persistent renal injury at 90 days following angiography, defined by an increase in SCr from baseline of  $\geq 50\%$ , in our primary composite endpoint. In preliminary analyses, we found that the development of CIAKI following angiography was associated with a prognostically meaningful, greater than 2-fold increase in the risk of developing a  $\geq 50\%$  increase in SCr at 90 days (OR = 2.4, 95% CI 1.9-3.0) confirming the strong link between CIAKI and persistent renal injury at 90

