## 2. Incidence of the 90-day endpoint and effects of our interventions

The events included in MAKE-D are death, need for acute dialysis, and persistent decline in kidney function. These events overlap. As previously discussed and summarized in Tables 4 and 5, most published randomized trials that investigated the proposed interventions did not report on these outcomes. However, for those that did track these events, acute dialysis was necessary in 0-7%, death occurred in 0-6%, and persistent decline in kidney function occurred in up to 19% of patients. Using the VA Austin database, we identified 25,909 Veterans who recently underwent coronary or non-coronary angiography who met our study entry criteria. Examining event rates at 90 days following angiography, we found that 1% died, 5% initiated dialysis, and 4% had a persistent increase in SCr of at least 50% (only about one-half of the patients had a measurement of SCr at 90 days). Overall, 8.7% had at least one of these events within 90 days. We therefore believe that the baseline incidence of MAKE-D in this patient population is 8.7%. Assuming an equal distribution of use of NAC versus no use of NAC and saline versus bicarbonate in this population with an overall event rate of 8.7%, a 25% reduction in the incidence of the composite primary outcome with bicarbonate (vs. saline) and with NAC (vs. placebo) would lead to the distribution of events with each treatment combination shown in Model 1. Using this approach, the overall sample size estimate, assuming a type 1 error of 0.025, 90% power, and 3% loss to follow-up, would be 6,500 subjects.

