3.5. Description of the Efficacy Endpoints

3.5.1. Primary Endpoints

The primary endpoint for the study is the composite end-point assessed at 90 days post index angiographic procedure and is comprised of the 3 events described below. Those subjects with at least one of these 3 events will be considered to have the primary study endpoint.

(1) Death from all causes to be verified by medical record and/or vital status registry documentation such as the VA Beneficiary Identification and Records Locator System, the National Center for Health Statistics National Death Index database, the Social Security Administration’s Death Master File.

(2) Acute dialysis defined as the initiation of any modality of renal replacement therapy, which includes intermittent hemodialysis, peritoneal dialysis, continuous renal replacement therapy, or prolonged intermittent renal replacement therapy.

(3) Persistent decline in kidney function defined as ≥50% increase in SCr at 90 days post procedure relative to baseline SCr collected pre-Angiography procedure, and derived as follows.

$$(SCr_{day90} / SCr_{pre-procedure}) * 100\% \geq 150\%$$

Both the initial 90 day specimen and the confirmatory sample processed at the Central Lab must establish a ≥50% increase in SCr to qualify as an endpoint event.

Please note:

1. 90 day blood sample is allowed to be collected within 6month window starting 90 days post index angiographic procedure.
2. 90 day blood sample is not necessary if pt is already on dialysis at day 90 post index angiographic procedure.

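### A dialysis start already planned at enrolment is neither excluded nor separable later, yet it scores as an acute primary event

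*Protocol*

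**What the plan says.** **Eligibility.** Protocol VII.G.3.b describes the range: "Given that we are proposing to enroll patients with Stage 3 and Stage 4 CKD (baseline eGFR 15-60 ml/min/1.73 m"². Protocol VI.A.2 excludes dialysis in progress (the item reads "Currently receiving hemodialysis, peritoneal dialysis, continuous renal replacement therapy, or sustained low efficiency dialysis (SLED"), stage 5 CKD, and a creatinine, if known, that changed by 25% or more in the three days before angiography. SAP Table 2 carries the same three items in short form. Neither list mentions a dialysis start that is planned but has not happened.

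**Endpoint.** Protocol VII.G.2 has the dialysis component "defined as the initiation of any modality of renal replacement therapy" within 90 days of the index procedure. SAP 3.5.1 agrees: "Acute dialysis defined as the initiation of any modality of renal replacement therapy". Neither asks for acute kidney injury, an indication or adjudication.

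**Rationale.** Protocol VII.G.3.b gives two grounds. Progression of stage 3–4 disease to chronic dialysis within 90 days would be unexpected without an acute change in its course. And 90 days is the conventional boundary between acute and chronic dialysis for patients dialysed in the setting of acute kidney injury. It concludes that dialysis within 90 days "as a component of the primary outcome in this study is, by definition, acute dialysis".

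**Data and analysis.** For renal replacement therapy, the 90-day assessment (protocol VII.H.10.b) lists the date of initiation and the duration. None of the five scenarios in SAP 5.3.5 concerns planned starts.

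**Planning rates.** Protocol XVII.A.2, for 25,909 Veterans: "we found that 1% died, 5% initiated dialysis, and 4% had a persistent increase in SCr of at least 50" per cent, with 8.7% having at least one event.

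**The concern.** A stable patient with an eGFR just above 15 and a chronic dialysis start already on the calendar meets every criterion. When that start happens, it is a primary event labelled acute.

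The two grounds in VII.G.3.b do not cover this patient. The first concerns unexpected progression, and a scheduled start is expected. The second is a convention for patients whose dialysis began because of acute kidney injury, so it presupposes what has to be shown.

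Neither bicarbonate nor NAC can prevent a start fixed before the angiogram. Such events fall equally in both arms of each comparison. They pull the relative reduction towards zero and are reported as acute dialysis. With only a date and a duration on file, nobody could later tell how many there were, or whether a null result was partly due to them.

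**Working it through.** **1. The gap.** This needs no arithmetic. The exclusions look at dialysis status and creatinine at baseline, the endpoint counts every initiation, and neither the 90-day fields nor the sensitivity scenarios identify a planned start.

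**2. What the planning rates suggest.** Inputs: deaths 1% and dialysis starts 5% (protocol XVII.A.2). Two cited mortality figures: "In patients who developed CIAKI that required renal replacement therapy, in-hospital mortality was 35.7" per cent (III.A.2.a, a PCI cohort), and "703 sustained dialysis-requiring AKI, of whom 295 (42%) died" (VII.G.3.b, hospitalised patients with eGFR of at least 45).

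Assign every death to a dialysis patient. Mortality among starters is then at most 1/5 = 20%. If acute starts carry mortality *m*:

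- acute starts ≤ deaths / *m*
- non-acute starts *u* ≥ dialysis starts − deaths / *m*

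The rates are rounded to whole per cents, so the least favourable limits for this argument are 1.49% deaths and 4.5% starts.

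**3. The plan's power, reproduced.** Evaluable per margin: 7,680 × 0.97 / 2 = 3,725. Boundaries are z = 3.18 at half the information and 2.25 at the end (protocol XVII.G). For 8.70% v 6.52%, the standard error is √[(0.0870 × 0.9130 + 0.0652 × 0.9348) / 3,725] = 0.00614, and the expected final z is 0.0218 / 0.00614 = 3.55. Two-look power is about 90%, as stated. For 8.70% v 6.99% it is about 69%, against 69.4% in Table 11. The plan's arithmetic is sound.

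**4. Conditional dilution.** Suppose the 25% effect applies only to the other events. The treated rate is *u* + 0.75 × (8.70 − *u*).

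| Case | *m* | Acute at most | *u* (share of starts) | Treated rate | Net reduction | Power |
|---|---|---|---|---|---|---|
| Face value, 1% and 5% | 35.7% | 2.80% | 2.20 points (44%) | 7.08% | 18.7% | 64% |
| Face value, 1% and 5% | 42% | 2.38% | 2.62 points (52%) | 7.18% | 17.5% | 57% |
| Rounding limits, 1.49% and 4.5% | 35.7% | 4.17% | 0.33 points (7%) | 6.61% | 24.1% | 88% |
| Rounding limits, 1.49% and 4.5% | 42% | 3.55% | 0.95 points (21%) | 6.76% | 22.3% | 81% |
| Acute-start mortality 20% or less | ≤ 20% | 5% | 0 | 6.52% | 25% | 90% |

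The table treats each non-acute start as a patient with no other component event. The components do overlap (1 + 5 + 4 = 10 against 8.7). Scaling *u* by 8.7/10 raises the two face-value powers to about 69% and 63%.

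**The case against.** Much of the case on the other side stands.

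- **The planning rates do not split acute from planned starts.** The inference borrows mortality from other populations. The 42% comes from hospitalised patients with eGFR of at least 45, whereas the trial takes non-diabetics only below 45 and diabetics only below 60. The 35.7% is in-hospital mortality, and the protocol gives no size or interval for that dialysis subgroup. At the rounding limits the discrepancy disappears once mortality is about 33% (1.49 / 4.5). A 5% dialysis rate also lies within the 0–7% that protocol XVII.A.2 reports from earlier trials. A reader might infer that many of the starts cannot have been acute; the documents do not show that.
- **The 25% is stated for all primary events.** Protocol XVII.A.2 says each intervention prevents a quarter of them, and III.A.2.e accepts that such events can arise without contrast injury. The 25% can be read as a net effect with unpreventable events already allowed for. A reader might infer that the trial has 57–64% power; that needs the extra assumption in step 4.
- **The extraction is described as matching the trial.** The protocol says these Veterans met the entry criteria and initiated dialysis. A reader might suspect that patients already on dialysis inflated the 8.7%; nothing in the text establishes this.
- **Counting any initiation is objective, and randomisation protects the test.** Both are true. Dialysis status at day 90 is also known, and the dialysis component is analysed separately (protocol XVII.E, item 4).

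None of this closes the gap. Duration, day-90 status and a component analysis do not reveal whether a start was planned before randomisation.

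**Conclusion.** The plan can score as acute a dialysis start that was arranged before the angiogram, and it has no means of finding out how often. That follows from the text alone.

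The size is unknown. On the planning rates and cited mortality, the non-acute share of starts is at least 44–52% at face value, at least 7–21% at the rounding limits, and possibly nil. The corresponding power is about 57–64%, 81–88% and 90%. These figures assume that the cited mortality transfers to this population, that all deaths were in dialysis patients, that non-acute starts do not overlap other events, and that the 25% effect applies only to the remaining events. They form a conditional range, not an estimate of the trial's power.

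There is no bias under the null hypothesis and no error in the sample size calculation. The harm is possible dilution of both comparisons and an inaccurate label. The change is worth making as a cheap improvement.

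**What to change.** 1. **Eligibility.** Add to protocol VI.A.2 and SAP Table 2 an exclusion for patients who, at enrolment, already have a chronic dialysis start planned within 90 days of the index procedure.
2. **Patients already enrolled.** For each start of renal replacement therapy, record from the chart, blinded to arm, whether it was planned before randomisation. Add a scenario to SAP 5.3.5 in which such starts are not counted as events. The primary analysis and its alpha stay as they are.
3. **Wording and planning rate.** Delete the claim in protocol VII.G.3.b that every start is acute by definition. Check that the extraction behind the 8.7% left out patients on dialysis or with eGFR below 15 at baseline. Restate the rate and the power only if the rate changes.

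Cost: one eligibility item, one CRF field, one extra sensitivity run and one database check. A few patients with eGFR 15–20 would be lost to enrolment.
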